7.2.1 Analysis Populations.....	27
7.2.2 Primary Objective	27
7.2.3 Secondary Objective	28
7.2.4 Exploratory Objective.....	29
7.2.5 Safety Monitoring Plan.....	29
7.3 Data Management Plan.....	29
7.3.1 Research Electronic Data Capture (REDCap).....	29
7.3.2 Role of the CDC Investigators in the Project.....	30
8 HUMAN SUBJECTS	30
8.1 Human Participants Involvement, Characteristics, and Design	30
8.2 Sources of Material.....	31
8.3 Potential Risks and Benefits.....	31

8.4 Adequacy of Protection	31
8.4.1 ClinicalTrials.gov Requirements	31
9.0 HUMAN SUBJECTS.....	31
9.1.1 Vulnerable Subjects.....	31
9.1.2 Vulnerable Subjects Research	32
REFERENCES	33

PROTOCOL SUMMARY

Title:	A Prospective Observational Study to Evaluate the Safety of COVID-19 Vaccination in Children and Adolescents
Phase:	Phase 4
Population:	Up to 320 male or female children and adolescents \geq 5 years to < 16 years
Clinical Sites:	Four: Duke University (Lead); Cincinnati Children's Hospital (Contributing); Kaiser Permanente (Contributing); Columbia University (Contributing)
Study Duration:	24 months
Participant Duration:	Approximately 7 months
Description of Study Procedures:	
This is a prospective, observational study to evaluate the safety of COVID-19 vaccination in children and adolescents receiving vaccine as part of standard of care. Children and adolescents who have not received any previous COVID-19 vaccines will be enrolled with their first dose. Children and adolescents who have completed their primary vaccine series will enroll with their age-appropriate booster dose based on current FDA indications and CDC recommendations.
 
Injection-site (local) and systemic reaction data and unsolicited adverse events will be assessed on vaccination day and daily during the 7 days following each COVID-19 vaccination dose using either identical web-based or paper memory aids, depending on study participant preference.
 
At 3 sites, serum samples will be collected for optional assessment of antibody titers to COVID-19. Each participant who opts in will have baseline (within 3 days of vaccination) serologies obtained. Serum samples will also be collected for immunogenicity assessments at 28 (+7) days after dose 2 or a booster dose.
 
All participants will be followed for 181 days after the last study dose 2 or a booster dose for serious adverse events (SAEs) and adverse events of special interest (AESI).

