EOM 1: Proportion of participants and legal guardians/parents with negative or positive perceptions of the vaccination experience based on participants responses to individual questions on the perceptions questionnaire

EOM 2: Assessment of primary outcome measures 1-6 in those with positive baseline COVID-19 serostatus versus those with a negative baseline serostatus

EOM 3: Proportion of participants with an adverse event of special interest through 6 months after dose 2 of COVID-19 vaccine or a booster dose

EOM 4: Proportion of participants with a serious adverse event through 6 months after dose 2 of COVID-19 vaccine or a booster dose

EOM 5a: The proportion of participants seropositive to SARS-CoV-2 variants tested prior to and following mRNA COVID-19 vaccine in a subset of children and adolescents

EOM 5b: The geometric mean ID₅₀ and ID₈₀ titers of neutralizing antibodies for each SARS-CoV-2 variant tested pre- and post-mRNA COVID-19 vaccine in a subset of child and adolescent participants.

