3 STUDY DESIGN

3.1 Main study design

This study is a prospective, observational study to evaluate the safety of COVID-19 vaccine in 320 children and adolescents 5 - < 16 years-old receiving the vaccine per standard of care. Children and adolescents who have not received any previous COVID-19 vaccines will be enrolled with their first dose. Children and adolescents who have completed their primary vaccine series will enroll with their age-appropriate booster dose based on current FDA indications and CDC recommendations. With Day 1 serving as the day of vaccination, participants will be followed through Day 7 (total 7 days) after each dose of COVID-19 vaccine for symptoms of reactogenicity as described in **Section 5.1**. Participants will also be followed for 7 days after each vaccination for unsolicited adverse events, through day 181 for SAEs, and through day 181 for adverse events of special interest.

Demographic and medical history data will be collected and COVID-19 serostatus determined at baseline, and parent perceptions of COVID-19 vaccine will be assessed on Day 7 after each dose of vaccine. Participant perceptions will also be collected on Day 7 in adolescents aged ≥ 12 years.

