Visit 2, COVID-19 Vaccine Dose 2 (+ 3 Days) (Clinic or Phone Visit)

- Confirm receipt of second dose of COVID vaccine
- Record any AEs, AESIs, SAEs, and concomitant medications and vaccinations as described in **Section 5.5**.
- Record clinical data related to COVID-19 diagnoses
- Confirm preferred method of contact for follow-up (telephone, email, or text reminder)
- Review instructions for use of thermometer, ruler, and memory aid completion.

Visit 2a, Days 1 - 7 Days after dose 2 (Phone Visit)

- Subjects/parent/LAR will complete their memory aid via paper or electronic entry at approximately the same time each day for days 1-7, study staff will review subject-entered data within the database or by phone contact
- For participants using REDCap web-based system:
 - Study staff will send daily reminders to fill out the symptom diary
 - Record clinical data related to COVID diagnoses
 - Study staff will review REDCap system to confirm data capture and assess for any AE, AESIs, or SAEs on day 3 and 7 after vaccine

- If any missing values, reported hives, or Grade 3 or greater events occurred, the study staff will use phone contact to gather more information
- The second parental and adolescent (if applicable) survey will be administered on day 7 after vaccine
- For participants using paper diary:
 - Study staff will call participants on day 3 after vaccine as a reminder to fill out the symptom diary
 - The second parental and adolescent (if applicable) survey will be administered on day 7 after vaccine
 - Study staff will call participants on day 7 (+ 3 days) after vaccine
 - Record symptom diary
 - Record COVID-19 diagnoses
 - Record second parental and adolescent (if applicable) survey

Visit 3, 28 Days (window days 29-35) after COVID-19 Dose 2 (Clinic Visit or Phone Visit)

- Clinic visit for optional post-vaccination blood draw for immunogenicity studies
- If no blood draw, may be a phone visit
- Review concomitant medications and vaccinations.
- Solicit for the occurrence of any adverse events of special interest or serious adverse events.

Visit 4, 180 days (window Days 174 - 188) after Dose 2 (Phone Visit)

- Record any SAEs or adverse events of special interest as described in **Section 5.5**
- Obtain concomitant medication and vaccine use

Table 2 describes the schedule of study visits for children enrolling with their COVID-19 booster dose.

Table 2: Schedule of events: Booster Dose

Procedure	Visit 1	Visit 1a	Visit 2	Visit 3

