- Dispense thermometer, ruler (in order to standardize measurements) and memory aid. Review instructions for use of thermometer, ruler, and memory aid completion. Preference will be to complete the memory aid electronically, with paper as a back-up.
- Confirm date of next scheduled study visit

Visit 1a, Days 1-7 after dose 1 (Phone Visit)

- Subjects/parent/LAR will complete their memory aid via paper or electronic entry at approximately the same time each day for days 1-7, study staff will review subject-entered data within the database or by phone contact
- For participants using REDCap web-based system:
 - Study staff will send daily reminders to fill out the symptom diary
 - Record clinical data related to COVID diagnoses
 - Study staff will review REDCap system to confirm data capture and assess for any AE, AESIs, or SAEs on day 3 and 7 after vaccine
 - If any missing values, reported hives, or Grade 3 events occurred, the study staff will use phone contact to gather more information
 - The parental and adolescent (if applicable) survey will be administered on day 7 after vaccine
 - Study staff will verify date of next study visit
- For participants using paper diary:
 - Study staff will call participants on day 3 after vaccine as a reminder to fill out the symptom diary
 - The parent and adolescent survey (if applicable) will be administered on day 7
 - Study staff will call participants on day 7 (+ 3 days)
 - Record symptom diary
 - Record COVID-19 diagnoses
 - Record parental and adolescent survey (if applicable)

Visit 2, 28 Days (window days 29-35) after COVID-19 Booster (Clinic Visit or Phone Visit)

- Clinic visit for optional post-vaccination blood draw for immunogenicity studies
- If no blood draw, may be a phone visit
- Review concomitant medications and vaccinations.

- Solicit for the occurrence of any adverse events of special interest or serious adverse events.

Visit 3, 180 days (window Days 174 - 188) after COVID-19 Booster (Phone Visit)

- Record any SAEs or adverse events of special interest as described in **Section 5.5**
- Obtain concomitant medication and vaccine use

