5.5 Reactogenicity & Safety Assessment

Frequency and occurrence of local and systemic reactogenicity events will be assessed through post-vaccination Day 7 using a standard memory aid. At the time of study enrollment, participants will be given a thermometer and instructed on using the memory aid to document oral temperatures and post-injection symptoms. Beginning on the evening following the first COVID-19 vaccination, LARs/participants will record the participants oral temperature using the study-supplied thermometer, the occurrence of solicited and unsolicited AEs, and concomitant medication use for the next 7 days (Day 1 – 7). Similarly, following the second COVID-19 vaccination, LARs/participants will record the participant's oral temperature using the study-supplied thermometer, the occurrence of solicited and unsolicited AEs, and concomitant medication use for the next 7 days. Temperature will be recorded at roughly the same time each day. If a temperature $> 100^{\circ}\text{F}$ (37.8°C) is recorded, a second measurement will be taken. If more than one temperature is taken on the same day, the highest temperature should be recorded. Fever will be defined as a measured temperature $\geq 100.4^{\circ}\text{F}$ (38°C). Participants will be queried during Visits 1a and 2a on solicited injection site adverse events, which will be classified as mild, moderate, or severe as described in **Table 4**. Participants will also be queried during Visits 1a and 2a on common post-injection systemic symptoms as described in **Table 5**.

Unsolicited adverse events (AEs) will be collected and reported for the 7 days following each vaccine. Any reports of new rash within 7 days after each dose will prompt a call from the study team to ascertain severity and the likelihood of an allergic reaction. Concomitant medication use, and concomitant vaccinations will be assessed through 29 days after dose 2 or a booster dose. Serious adverse events (SAEs), adverse events of special interest (AESIs) and unscheduled medical care for COVID-19 illness will be assessed at 29 days after dose 2 of COVID-19 vaccine or a booster dose and through the end of the study (181 days after dose 2).

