Unsolicited adverse events, AESIs and SAEs will be graded as described in **Table 6**. Participants who report severe solicited adverse events or express any concern about symptoms/unsolicited events will be encouraged to follow up with their primary care provider. Study staff will assist with coordination of referral appointments as necessary. Parent/LAR will be asked to agree to the release of information to obtain and review medical records for any unscheduled medical appointments, including clinic visits and telehealth visits, through 29 days after the second dose. Frequency and occurrence of serious AEs (SAEs), AESIs and unscheduled medical care for COVID-19 illness will be assessed through 181 days after dose 2 or a booster dose.

Table 4: Injection-site Reactogenicity			
Symptom	Mild (Grade 1)	Moderate (Grade 2)	Severe (Grade 3)
Pain	Does not interfere with activity	Interferes with activity	Prevents daily activity
Tenderness	Does not interfere with activity	Interferes with activity	Prevents daily activity
Underarm or groin swelling on same side as vaccine	Does not interfere with activity	Interferes with activity	Prevents daily activity
Swelling	5-11 years: 5-20 mm	5-11 years: 21-70 mm	5-11 years: >70 mm
	12 years >: 20-50 mm	12 years >: 51 - 100 mm	12 years: >100 mm
Redness	5-11 years: 5-20 mm	5-11 years: 21-70 mm	5-11 years: >70 mm
	12 years >: 20-50 mm	12 years >: 51 - 100 mm	12 years: >100 mm

Table 5: Systemic Reactogenicity			
Systemic	Mild (Grade 1)	Moderate (Grade 2)	Severe (Grade 3)
Fever (°C)	≥ 38.0 – 38.4 ≥ 100.4 - < 101.1° F	>38.4 – 38.9 ≥ 101.1 - < 102° F	> 38.9° C ≥ 102° F

Table 5: Systemic Reactogenicity			
Feverishness	Does not interfere with activity	Some interference with activity	Prevents daily routine activity
Chills	Does not interfere with activity	Some interference with activity	Prevents daily routine activity
Headache	Does not interfere with activity	Some interference with activity	Prevents daily routine activity
Fatigue	Does not interfere with activity	Some interference with activity	Prevents daily routine activity
Muscle Pain	Does not interfere with activity	Some interference with activity	Prevents daily routine activity
Joint Pain	Does not interfere with activity	Some interference with activity	Prevents daily routine activity
Vomiting	Does not interfere with activity	Some interference with activity	Prevents daily routine activity

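### Section 5.5 does not consistently support the 181-day safety follow-up behind EOM 3 and EOM 4: its stated records release ends at Day 29 and omits the booster

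*Combined protocol and SAP*

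**What the plan says.** The follow-up horizon is stated several times and agrees. On serious adverse events (SAEs) and adverse events of special interest (AESIs), the Protocol Summary says "All participants will be followed for 181 days after the last study dose 2 or a booster dose". Section 3.1 has "through day 181 for SAEs, and through day 181 for adverse events of special interest". In Section 2, EOM 3 is the "Proportion of participants with an adverse event of special interest through 6 months after dose 2 of COVID-19 vaccine or a booster dose", and EOM 4 is its counterpart for SAEs.

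The supporting procedures vary:

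- **Records release.** In the Section 5.5 paragraph before Table 4, parents are asked to let the study obtain and review "medical records for any unscheduled medical appointments, including clinic visits and telehealth visits, through 29 days after the second dose". The next sentence says that SAEs, AESIs and unscheduled COVID-19 care "will be assessed through 181 days after dose 2 or a booster dose".
- **Final contact.** Section 5.1 gives "Visit 4, 180 days (window Days 174 - 188) after Dose 2 (Phone Visit" for the primary series and "Visit 3, 180 days (window Days 174 - 188) after COVID-19 Booster (Phone Visit" for booster enrollees. Tables 1 and 2 give 181 (+/- 7).
- **Vaccine recording.** Section 5.5 states: "Concomitant medication use, and concomitant vaccinations will be assessed through 29 days after dose 2 or a booster dose". Tables 1 and 2 mark this item at every visit, and both final-visit lists in Section 5.1 include it.

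Three other provisions bear on the point. Section 5.1 obtains a medical record release at Visit 1, with no end date. Section 5.3 has the medical record reviewed for SAEs and AESIs throughout the study. Section 8.2 names record review and visits as the sources for these events.

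**The concern.** Two adjacent sentences in Section 5.5 give different time spans for linked activities, and only the longer one names the booster. Section 3.1 enrols booster recipients after they have completed their primary series, so for them the second dose came before the study. Read literally, their release period has no usable end.

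This matters because Section 4.3 also recruits at public vaccination sites, so some children may receive later care elsewhere. No contact is scheduled between the Day 29 visit and the final call, about five months later. If outside records cannot be obtained for that period, EOM 3 and EOM 4 rest for those children on the study sites' own records and on recall at one call. So would the narratives of late myocarditis, pericarditis or MIS-C that go to the safety review panel (Section 7.2.5). Missed events would lower the six-month proportions.

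**Working it through.** **Inputs.** End of surveillance: Day 181 (Section 3.1). End of the stated release: 29 days after the second dose (Section 5.5). Final contact: 181 +/- 7 (Tables 1 and 2). Planned enrolment: 320 (Section 3.1). The documents give no six-month event risk; I assume 0.25% to 2%, with a constant hazard.

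**1. The plan's own window.** 181 − 7 = 174 and 181 + 7 = 188, so the visit text and the tables agree. Day 1 is the day of vaccination, so Day 181 is 180 days later, which matches the visit headings. I read 29 and 181 days after a dose as Day 29 and Day 181. If they are elapsed days instead, both end points move by one. The difference below stays at 152 days, and the largest shortfall of the final call becomes 182 − 174 = 8 days instead of 7.

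**2. Span of the stated release.** 181 − 29 = 152 days lie beyond it; 152/181 = 84%. It covers 29/181 = 16%.

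**3. What else covers Days 30–181.**

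| Item assessed to Day 181 | Other support in the protocol | What remains open |
|---|---|---|
| SAEs and AESIs | Record review (5.3, 8.2), undated Visit 1 release (5.1), final call | Whether records of care outside the study sites can be obtained after Day 29 |
| Unscheduled COVID-19 care | COVID-19 disease history row in Tables 1 and 2, described in Table 3 as diagnoses | Care itself: absent from 5.3, from 8.2 and from the final-visit lists |
| Booster enrollees | Named in the 181-day sentence | Not named in the release sentence |

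**4. Early final call.** The largest shortfall is 181 − 174 = 7 days: 7/181 = 3.9% of follow-up, or 7/152 = 4.6% of Days 30–181. If calls were spread evenly over the 15 days 174–188 (assumption), 7/15 = 47% would fall before Day 181. The mean shortfall would be (7+6+5+4+3+2+1)/15 = 28/15 = 1.9 days per child.

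**5. Scale in events.** Expected participants with an event over six months: 320 × 0.0025 = 0.8 to 320 × 0.02 = 6.4.

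- In Days 175–181, if every call were on Day 174: multiply by 7/181, giving 0.03 to 0.25.
- In Days 30–181: multiply by 152/181, giving 0.7 to 5.4.

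The second range counts events that occur in that period, not events that would be missed.

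**6. Vaccine recording.** One sentence in Section 5.5 stops at Day 29. Tables 1 and 2 and both final-visit lists continue to Day 181, and Section 5.3 documents vaccines given during the study period. The conflict concerns exposure data; it does not shorten the capture of SAEs or AESIs.

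**The case against.** The best defence is that 181-day ascertainment of SAEs and AESIs is in the plan: record review without a Day 29 limit, an undated release at Visit 1 and a final safety contact. The 29-day sentence concerns unscheduled appointments and follows text on solicited symptoms and primary-care referral. It does not say that hospital, SAE or AESI records are limited to 29 days. The least supported item, unscheduled COVID-19 care, feeds no outcome measure. The missing booster may be a drafting slip, since neighbouring sentences name it. POM 5 and POM 6 end at Day 29 and are untouched.

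Most of this stands, and it rules out several stronger readings that a reader might infer:

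- That the six-month follow-up is not delivered. The provisions above contradict this.
- That 84% of follow-up is unobserved. That figure is only the share of days beyond the stated release limit.
- That a child called on Day 174 is counted as fully followed. The text gives no counting rule, and Section 7.2.4 leaves exploratory analyses to a separate plan.
- That a further COVID-19 dose after Day 29 would be unknown. This would require ignoring the tables and the visit lists.

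The defence does not remove the conflict. Section 5.5 is the only place that gives the release a time limit, and the Visit 1 release depends on site IRB requirements, so a site could write 29 days into its form. Nothing says that outside records can be obtained after that.

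**Conclusion.** The point holds as an inconsistency that should be corrected, with medium confidence. The stated release and the 181-day assessment must be reconciled in both cohorts. The gap is clear for unscheduled COVID-19 care. For SAEs and AESIs it is limited to records held outside the study sites, and its effect on EOM 3 and EOM 4 cannot be sized because the documents do not say how much care is given elsewhere. The consent pages are not available, so this is a finding about the protocol text, not about the form that parents sign.

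The early call is minor: under the assumptions above, fewer than 0.3 participants would be expected to have an event in the affected days. The vaccine-recording conflict is also minor, but a further COVID-19 dose should be known when a late event is described. Only exploratory, descriptive outcomes are affected.

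**What to change.** 1. In Section 5.5, state that the release covers records of SAEs, AESIs and unscheduled care through 181 days after dose 2 or the booster, consistent with the Visit 1 release in Section 5.1 and with Sections 5.3 and 8.2. Check each site's consent form against this.
2. Minor: make the final contact forward-only, for example Day 181 (+7), asking about events through Day 181. This brings the shortfall to zero and leaves the latest permitted date at Day 188. Alternatively, keep the window and carry the record review to Day 181 for children called earlier.
3. Minor: align the Day 29 limit on vaccine recording in Section 5.5 with Tables 1 and 2 and the final-visit lists.

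The cost is protocol wording and, where a site's form carries the 29-day limit, a consent amendment through that site's IRB and a revised release for families already enrolled. The forward-only option gives staff a narrower call window, 8 days instead of 15. Sample size and the primary analysis do not change.

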2 STUDY OBJECTIVES

Primary Objective (PO):

To characterize the safety of authorized and recommended COVID-19 vaccines among children and adolescent participants

Secondary Objective (SO):

To assess the safety of simultaneous administration of COVID-19 vaccine with other routinely recommended vaccines among children and adolescent participants

Exploratory Objectives (EO):

EO 1: To assess adolescent and parent perceptions of the COVID-19 vaccine recommendations and experience with receipt of the vaccine

EO 2: To assess the safety of COVID-19 vaccine stratified by baseline COVID-19 serostatus (positive versus negative) in a subset of child and adolescent participants

EO 3: To assess adverse events of special interest through 6 months after dose 2 of COVID-19 vaccine or a booster dose

EO 4: To assess serious adverse events through 6 months after dose 2 of COVID-19 vaccine or a booster dose

EO 5: To assess immune responses to SARS-CoV-2 antigens after COVID-19 vaccine

Primary Outcome Measures (POM):

POM 1: Proportion of participants with defined local or systemic reactogenicity events (stratified according to severity and in total) on days 1-7 after each dose of COVID-19 vaccine

POM 2: Proportion of participants with at least one severe (Grade 3) solicited local or systemic reactogenicity event on days 1-7 after each dose of COVID-19 vaccine

POM 3: Proportion of participants with at least one moderate-to-severe (Grade 2-3) solicited local or systemic reactogenicity event on days 1-7 after each dose of COVID-19 vaccine

POM 4: Proportion of participants with an unsolicited adverse event on days 1-7 after each dose of COVID-19 vaccine

POM 5: Proportion of participants with an adverse event of special interest through 29 days after dose 2 of COVID-19 vaccine or a booster dose

POM 6: Proportion of participants with at least one serious adverse event occurring through 29 days after dose 2 of COVID-19 vaccine or a booster dose and a description of the serious adverse events

Secondary Outcome Measure (SOM):

SOM: Assessment of primary outcome measures 1-6 in those receiving other routinely recommended vaccines simultaneously with each dose COVID-19 vaccine versus those receiving COVID-19 vaccine alone

Exploratory Outcome Measures (EOM):

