Diarrhea	Does not interfere with activity	Some interference with activity	Prevents daily routine activity
Nausea	Does not interfere with activity	Some interference with activity	Prevents daily routine activity
Facial or lip swelling	Does not interfere with activity	Some interference with activity	Prevents daily routine activity

Table 6: Grading for Unsolicited Adverse Events, AESIs and SAEs			
Mild (Grade 1)	Moderate (Grade 2)	Severe (Grade 3)	
Does not interfere with activity	Some interference with activity	Prevents daily routine activity	

In this study, COVID-19 vaccination is not a study procedure. COVID-19 vaccine administration will be given per standard of care to children and adolescents receiving vaccine under an EUA by the Food and Drug Administration. Published studies in children and adolescents found no vaccine-related serious adverse events in children or adolescents receiving BNT162b2 (3-5). Lymphadenopathy was identified as an adverse event occurring more frequently in BNT162b2 vs. placebo groups during clinical trials (11). Post-authorization vaccine safety data have identified two safety concerns that rarely can occur after vaccination: severe allergic reactions, including anaphylaxis, and myocarditis and pericarditis (11). Therefore, we do not anticipate any significant issue with serious adverse events (SAEs). Nevertheless, we will monitor study participants for SAEs during the protocol-defined surveillance period of 6 months after second dose or a booster dose. SAEs will be reported to the CDC and all participating IRBs according to institutional requirements.

Perceptions of COVID-19 vaccine

At Day 7 (+3) following each of the vaccination visits we will assess adolescent (ages 12 to < 16) and parent/LAR perceptions of the COVID-19 vaccine recommendations and experience with receipt of the vaccine. Questions are provided in **Tables 7 and 8** below. We will use a Likert scale (strongly agree, agree, neither, disagree, strongly disagree) to assess response to the questions about concerns regarding COVID-19 vaccine safety. As noted, adolescent and parent perceptions regarding vaccine receipt will be assessed at the reactogenicity assessment visits after each vaccine.

Table 7 Parental /LAR Perceptions of COVID-19 Vaccine Recommendations and Receipt

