Vaccine Recommendation: What is your primary source of information about the COVID-19 vaccine (Choose one or more options): 
 Television Internet Radio Social media Family and friends Your child's doctor or nurse Another healthcare provider Your child's school Another source (please explain):
Vaccine Recommendation: COVID-19 vaccines have been adequately tested in adolescents and children
Vaccine Recommendation: COVID-19 vaccine should be required for school entry
Vaccine Receipt: Reactions at the vaccine site (pain, redness) were similar to other vaccines my child has received
Vaccine Receipt: Other reactions (fever, tiredness, muscle aches) were similar to other vaccines my child has received
Vaccine Receipt: I prefer that my child receives the COVID-19 vaccine on the same day as other vaccines

Table 8: Adolescent Perceptions (Ages 12 to < 16 years) of COVID-19 Vaccine Recommendations and Receipt

Vaccine Recommendation: What is your primary source of information about the COVID vaccine (Choose one or more option):

- Television
- Internet
- Radio
- Social media
- Family and friends
- Your doctor or nurse
- Another healthcare provider
- Your school
- Another source (please explain):

Vaccine Recommendation: COVID-19 vaccines have been tested enough in adolescents

Vaccine Recommendation: COVID-19 vaccine should be needed to go to school

Vaccine Receipt: My reaction where I got the vaccine in the arm (pain, redness) were about the same to other vaccines I have received

Vaccine Receipt: Other reactions (fever, tiredness, muscle aches) were about the same to other vaccines I have received

Vaccine Receipt: I prefer to receive COVID-19 vaccine on the same day as other vaccines

Causality (relatedness) Assessment

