7.1 Sample Size and Power Estimation

Because this is an observational study with no randomization of subjects into treatment groups, there will be no formal statistical power or sample size calculation.

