7.2.4 Exploratory Objective

Exploratory Objective- To assess immune responses to SARS-CoV-2 antigens after COVID-19 vaccine.

The analysis for exploratory objectives will be detailed in the comprehensive Statistical Analysis Plan. .

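### The survey asks for the primary source of vaccine information but accepts several answers, so the primary source is lost for anyone who ticks more than one

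*Combined protocol and SAP*

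**What the plan says.** The perceptions survey is set out in Section 5.5, Tables 7 (parent/LAR) and 8 (ages 12 to under 16). It is given about day 7 after each study dose, so twice for primary-series enrollees and once for booster enrollees.

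The first item in Table 7 reads "What is your primary source of information about the COVID-19 vaccine (Choose one or more options". The first item in Table 8 reads "What is your primary source of information about the COVID vaccine (Choose one or more option". Each is followed by nine parallel options, the last an open-ended other source. The remaining five items in each table are agreement statements.

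For response format, Section 5.5 says "We will use a Likert scale (strongly agree, agree, neither, disagree, strongly disagree", and ties that scale to the questions on vaccine-safety concerns. Nothing asks respondents to rank the sources they tick or to mark the main one.

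The survey serves EO 1 in Section 2: "To assess adolescent and parent perceptions of the COVID-19 vaccine recommendations and experience with receipt of the vaccine". The matching outcome measure, EOM 1, is "Proportion of participants and legal guardians/parents with negative or positive perceptions of the vaccination experience", based on answers to individual survey questions. On analysis, Section 7.2.4 says only "The analysis for exploratory objectives will be detailed in the comprehensive Statistical Analysis Plan"; Section 7.2.3 ends with a similar deferral.

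**The concern.** The stem and the instruction ask for different things. Some respondents will follow the stem and tick one source. Others will follow the instruction and tick every source they use. The completed form does not show which reading was taken, so a single tick may mean *my only source* or *my main source among several*.

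The plan's intended use of the item is therefore at risk in two ways. The distribution of primary sources is incomplete, because it is missing for everyone with two or more ticks. The prevalence of use of each source is also uncertain, because respondents who followed the stem may have left out sources they use. The gap arises when the data are collected, so deferring the analysis to a later plan does not close it.

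**Working it through.** The documents state no figure on this point, so there is nothing to reproduce. Section 7.1 says "there will be no formal statistical power or sample size calculation", and alpha, power and dropout do not bear on the question. The check sets the texts side by side and then asks what the data could support.

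**Step 1: stem against instruction.** Both tables ask for a singular primary source and both allow one or more answers. The conflict lies in the wording of the question itself, and it is the same in both tables apart from minor differences of phrasing. The bullet style beside the options should not be taken as evidence that the form enforces a single choice.

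**Step 2: does anything else resolve it?** The Likert scale does not fit a list of sources. There is no ranking, no follow-up item and no rule for multiple ticks in Section 5.5 or Section 7. The plan to which exploratory analysis is deferred could say how to tabulate multiple ticks, but it could not recover a choice that was never recorded.

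**Step 3: which answer patterns identify a primary source?** With nine options and at least one tick, the number of possible patterns is 2^9 − 1 = 512 − 1 = 511. Nine of these are single ticks and identify a primary source. The other 511 − 9 = 502 do not. This counts patterns, not respondents, and says nothing about how often each will occur.

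**Step 4: what can be estimated for a given source Y?** Let N be the number of respondents, a the number who ticked Y alone, b the number who ticked Y with others, and c the number who ticked one source other than Y. Assume that a respondent's primary source is among those ticked.

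- Proportion whose primary source is Y: between a/N and (a + b)/N. The width, b/N, comes entirely from multiple ticks.
- Proportion who use Y at all: between (a + b)/N and (a + b + c)/N. The width, c/N, comes from single ticks that may conceal other sources.

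The first interval closes only if nobody ticks Y together with another source. The second closes only if nobody gives a single tick for a different source. A mixture of readings leaves both open.

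**Step 5: how many respondents?** If a share s tick two or more, the primary source is missing for s × N at that survey. With at most 320 parents, this runs from 0 (s = 0) to 320 (s = 1). The documents do not narrow s, so no figure inside that range is claimed.

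**Step 6: which outcomes are touched?** A source of information has no positive or negative value, so the item does not enter the EOM 1 proportion. The five agreement items in each table are unaffected. None of the primary outcome measures, nor the secondary comparison by concomitant vaccination, uses it.

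**The case against.** The best defence is that this is one loosely worded item in an exploratory survey. No named outcome measure depends on it, and the proportion selecting each source can be reported as an ordinary multiple-response result with the question wording stated. Percentages that add to more than 100% are normal for such items. This largely stands and fixes the weight of the point. It does not remove the ambiguity, since the proportion selecting a source is neither the proportion using it nor the proportion relying on it mainly.

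Three stronger readings are tempting, and the documents do not support them.

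- A reader might infer that the primary source cannot be identified at all. It can, for every respondent who ticks one option.
- A reader might infer that parent and adolescent answers cannot be compared. Both groups receive essentially the same stem, instruction and options. A comparison would be distorted only if the groups resolved the wording differently, and nothing in the documents shows that they would.
- A reader might want a number of parents affected, by assuming some share of multiple ticks and multiplying by 320. Nothing in the documents supports any particular share.

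It is also fair to say that a change has a cost beyond editing. Section 8.1 makes each site responsible for submitting written study materials to its own IRB, and a mid-study change breaks the continuity of the item.

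**Conclusion.** The point holds, as a minor one. In both tables the item loses the primary source for any respondent who ticks more than one option, and its counts mix two quantities in unknown proportion. No later analysis rule can repair this. The effect is confined to one exploratory item under EO 1; the EOM 1 proportion and the primary and secondary outcomes are unaffected.

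The conclusion rests on the wording of the two items and on the absence of any ranking or main-source question elsewhere in the protocol. It does not depend on an assumed frequency of multiple ticks, although its practical size does. If almost everyone ticks one option, little is lost on primary source; if many tick several, the item cannot describe primary sources for the sample.

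**What to change.** Decide which quantity is wanted, and change Tables 7 and 8 in the same way. Either option resolves the conflict.

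- **Main source wanted:** make the item single choice (*main source, choose one*). If other sources are also of interest, add a separate item (*other sources used, choose all that apply*) and tabulate the two separately.
- **All sources wanted:** drop the word *primary*, keep the existing response rule, and report a multiple-response item as the percentage of respondents selecting each source.

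The cost is a wording edit and a REDCap field change, matched on the paper form, plus submission of the revised survey to the IRBs of the four sites. No visits or participants are added. If the change is made after enrolment has begun, tabulate responses before and after it separately. For primary-series participants the change may fall between the dose 1 and dose 2 surveys, so the version used should be recorded with each response.
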